5.1.3 Treatment Period

After meeting the eligibility criteria, subjects will be enrolled via IRT into a treatment arm. All subjects will begin study drugs (venetoclax/placebo and LDAC) on Cycle 1 Day 1. Subjects in Arm A will receive venetoclax orally QD plus LDAC SC QD beginning on Cycle 1 Day 1. Venetoclax should be taken within 30 minutes after completion of a meal (preferably breakfast). Subjects in Arm B will receive placebo orally QD plus LDAC SC QD beginning on Cycle 1 Day 1. Placebo should be taken within 30 minutes after completion of a meal (preferably breakfast). Subjects will receive LDAC on Days 1 – 10 of each cycle beginning on Cycle 1.

Dosing Schedule Overview – for Venetoclax/Placebo and LDAC

Venetoclax or placebo for venetoclax will be administered with a 4-day ramp up beginning with 100 mg dose on Day 1, 200 mg dose on Day 2, 400 mg dose on Day 3 and 600 mg dose on Day 4 of Cycle 1. Subjects will be hospitalized during the venetoclax ramp-up period during Cycle 1 (i.e., Day 1 through Day 5). Subjects will remain in the hospital for at least 24 hours after reaching the final dose of venetoclax on Day 4. Venetoclax or placebo for venetoclax will be continued at 600 mg daily thereafter. LDAC will be administered SC daily per protocol at 20 mg/m² daily on Days 1 – 10 of each cycle.

Figure 1. Dosing Schematic

Cycle = 28 days. For dosing delay and/or duration guidelines please refer to Section 6.1.7.

Cycle Length – 28 Days

- Venetoclax 600 mg or Placebo 600 mg QD on Days 1 – 28
- LDAC 20 mg/m² SC Daily on Days 1 – 10

Subjects will continue their study treatment until documented disease progression per Investigator assessment, unacceptable toxicity, withdrawal of consent, or the subject meets other protocol criteria for discontinuation (whichever occurs first). Study treatments may be administered in the hospital, clinic or in a non-hospital/clinic environment (home), as allowed per local regulations.

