5.4 Removal of Subjects from Therapy or Assessment

5.4.1 Discontinuation of Individual Subjects from Treatment

Each subject has the right to withdraw from the study at any time. In addition, the investigator will discontinue a subject from the study at any time if the investigator considers it necessary for any reason including:

- The investigator believes it is in the best interest of the subject;
- The subject's response to therapy is unsatisfactory, as evidenced by progression of disease while on study drug;

- The subject experiences toxicities related to study drug that require more than a 4-week (one cycle) dose interruption of venetoclax or LDAC, in the absence of clinical benefit;
- The subject requires any radiotherapy or alternate chemotherapy during the study period (with the exception of hydroxyurea [allowed in first month only]);
- The occurrence of an adverse event that precludes further LDAC administration;
- Noncompliance with the protocol.
- Treatment failure, defined as failure to achieve CR, CRi, PR, or MLFS.
- The subject becomes pregnant while on study drug.

Treatment will be continued as long as the patient continues to derive clinical benefit or until documented disease progression or develops unacceptable toxicity.

Accordingly, subjects may, in rare occasions, continue treatment after documented disease progression if the investigator believes it is in the best interest of the patient.

Following the final analysis results, the subjects will be unblinded by the Sponsor to the treatment assignment and subjects will be allowed to continue the assigned treatment arm as long as they derive clinical benefit from the treatment in the opinion of the investigator, or until transition to commercial supply is available, or until protocol criteria for discontinuation is met.

The investigator or study site personnel will inform AbbVie prior to discontinuing a subject from the study by contacting the Medical Monitor as identified in Section 7.0. All subjects will be included for analysis of safety data.

In the event that a subject withdraws or is discontinued from the study, the reason(s) for the discontinuation from the study and the primary reason will be recorded and a Final Treatment Visit along with all necessary procedures per [Appendix C](#) (will be performed as soon as possible after discontinuation from the study). The subject would then enter

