5.6 Discussion and Justification of Study Design

5.6.1 Discussion of Study Design and Choice of Control Groups

This is a multicenter, randomized, double blind study to evaluate the efficacy and safety of venetoclax plus LDAC compared to an active control of placebo plus LDAC. The choice of the control group allows for a double blind assessment of the contribution of venetoclax to the safety and efficacy of the backbone regimen LDAC.

LDAC is a standard treatment option in many countries worldwide and is often referred to as low intensity therapy for AML. Low intensity therapy, such as LDAC, azacitidine, or decitabine are considered appropriate treatment approaches by the National Cooperative Cancer Network (NCCN)²⁶ and European LeukemiaNet (ELN)²⁸ for patients who are not candidates for intensive chemotherapy induction or HSCT. Two Phase 3 trials have compared azacitidine²⁹ and decitabine³⁰ to physician's choice therapy for older patients with newly diagnosed AML to evaluate if either provided a statistically significantly longer survival when given as the initial treatment for AML. To date, neither agent has been found to provide a significantly longer survival for patients with newly diagnosed AML than for those randomized to physician choice. The most common treatment, in both studies, amongst the patients randomized to physician choice was LDAC. The response rates to LDAC when administered as monotherapy are substantially lower than what is seen in Study M14-387 in combination with venetoclax and preliminary projections for median survival times also appear better than for the aforementioned historical experiences with LDAC monotherapy.³¹

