8.1.7.2 Adverse Events

Analyses of adverse events will include only "treatment-emergent" events, i.e., those that have an onset on or after the day of the first dose of venetoclax or LDAC, whichever comes first. Analyses will not include those that have an onset greater than 30 days after the last dose of venetoclax or LDAC, whichever comes later. Treatment-emergent adverse events will be summarized by preferred terms within a System Organ Class according to the Medical Dictionary for Regulatory Activities (MedDRA) dictionary. In

addition, the percentage of subjects experiencing an adverse event at a given NCI CTCAE Version 4.03 toxicity grade and relationship to study drug will be provided.

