9.0 Study Treatment Exposure and Compliance

The duration of exposure to venetoclax/placebo will be summarized by treatment arm, for safety analysis set as described in Section 5.1. Duration of exposure is defined for each subject as (last dose date – first dose date) + 1. Duration of exposure will be summarized using the following statistics (months): sample size (N), mean, standard deviation, median, and range. In addition, the number and percentage of subjects exposed to venetoclax/placebo will be summarized for the following categories of exposure duration:

- 0 to 4 weeks (0 to 28 days),
- > 4 weeks to 8 weeks (28 to 56 days),
- > 8 weeks to 12 weeks (57 to 84 days),
- > 12 weeks to 16 weeks (85 to 112 days),
- > 16 weeks to 20 weeks (113 to 140 days),
- > 20 weeks to 24 weeks (141 to 168 days),
- > 24 weeks to 28 weeks (169 to 196 days),
- > 28 weeks to 32 weeks (197 to 224 days),
- > 32 weeks to 36 weeks (225 to 252 days),

- > 36 weeks to 52 weeks (253 to 364 days),
- > 52 weeks (> 364 days).

The number of cycles that subjects are exposed to study drug will be summarized by treatment arm. There will be no statistical comparison for the study treatment exposure between the two treatment arms.

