11.1 Analysis of Treatment-Emergent Adverse Events

All summaries/analyses involving AEs will include treatment-emergent adverse events (TEAE) only, unless otherwise specified. TEAEs are defined as any adverse event with onset after the first dose of study drug and no more than 30 days after the last dose of

study drug. Events where the onset date is the same as the study drug start date are assumed to be treatment-emergent. If an incomplete or missing onset date was collected for an AE, the AE will be assumed to be treatment-emergent unless there is evidence that confirms that the AE was not treatment-emergent (e.g., the AE end date was prior to the date of the first dose of study drug).

For summaries of AEs related (reasonable possibility) to study drug, at each level of summation (overall, SOC, and PT) each subject is counted only once. If a subject has an AE with unknown relationship, then the subject will be counted in the relationship category of "unknown," even if the subject has another occurrence of the same event with a relationship of "no reasonable possibility" present. The only exception is if the subject has another occurrence of the same AE with the relationship of "reasonable possibility." In this case, the subject will be counted under the reasonable possibility category.

Adverse event data will be summarized and presented using primary MedDRA system organ classes (SOCs) and preferred terms (PTs) according to the MedDRA coding dictionary version 21.0 or higher.

The number and percentage of subjects experiencing treatment-emergent adverse events will be summarized for the following adverse event summaries:

- Any treatment-emergent adverse event.
- Any treatment-emergent adverse event with NCI toxicity (CTCAE V4.03) grade 3, 4, or 5 adverse events.
- Any treatment-emergent serious adverse event.
- Any treatment-emergent adverse event with reasonable possibility related to venetoclax/placebo by the investigator.
- Any treatment-emergent adverse event leading to discontinuation of venetoclax/placebo.
- Any treatment-emergent adverse event leading to venetoclax/placebo interruption.

- Any treatment-emergent adverse event leading to venetoclax/placebo reduction.
- Any treatment-emergent adverse event with reasonable possibility related to LDAC by the investigator.
- Any treatment-emergent adverse event leading to discontinuation of LDAC.
- Any treatment-emergent adverse event leading to LDAC interruption.

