- Any treatment-emergent adverse event leading to LDAC reduction.
- Any treatment-emergent adverse event leading to death.

In addition, the treatment emergent AEs and serious AEs for selected grouped preferred terms (PTs) including, but not limited to, those listed in [Table 9](#), will be summarized.

Table 9. Selected Adverse Events

Selected Adverse Events	Search Criteria
Tumor Lysis Syndrome (AE)	SMQ – "Tumor Lysis Syndrome" (narrow)
Grade \geq 3 neutropenia	PT terms – "neutropenia," "neutrophil count decreased," "febrile neutropenia," "agranulocytosis," "neutropenic infection," and "neutropenic sepsis"
Grade \geq 3 infection, including opportunistic infections	SOC of "infections and infestations"
Haemorrhages	SMQ – "Haemorrhages" (narrow)
Anemia	PT terms – "Anaemia" and "Haemoglobin decreased"
Thrombocytopenia	PT terms – "Thrombocytopenia" and "Platelet count decreased"

There will be no statistical comparison for TEAEs between two treatment arms.

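### Adverse events are shown by arm only as crude percentages over a window that follows treatment duration; if treatment lasts longer on venetoclax, events that persist through treatment will look more frequent there even at equal hazards

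*SAP*

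**What the plan says.** **Measure.** SAP 11.1: "The number and percentage of subjects experiencing treatment-emergent adverse events will be summarized for the following adverse event summaries". Protocol 8.1.7.2 is consistent with this and plans "the percentage of subjects experiencing an adverse event at a given NCI CTCAE Version 4.03 toxicity grade".

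**Window.** SAP 11.1 runs it from first dosing to a month beyond final dosing: "TEAEs are defined as any adverse event with onset after the first dose of study drug and no more than 30 days after the last". SAP 6.0 takes the last dose as the later of venetoclax/placebo and LDAC, and applies one data cutoff to efficacy and safety.

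**Comparison.** SAP 11.1: "There will be no statistical comparison for TEAEs between two treatment arms".

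**Exposure.** SAP 9.0: "The duration of exposure to venetoclax/placebo will be summarized by treatment arm". The number of cycles is also summarized. Neither is used as a denominator for adverse events.

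**Treatment duration.** It is open-ended. Protocol 5.1.3: "Subjects will continue their study treatment until documented disease progression per Investigator assessment, unacceptable toxicity, withdrawal of consent" and other criteria. Protocol 5.4.1 lists among the reasons to stop: "Treatment failure, defined as failure to achieve CR, CRi, PR, or MLFS".

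**Expected difference between arms.** Protocol 5.6.1: "The response rates to LDAC when administered as monotherapy are substantially lower than what is seen in Study M14-387 in combination with venetoclax". SAP 4.3 plans on median survival of 6 v 11 months.

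Neither document plans adverse event rates per unit of time, time to first event, cumulative incidence, or adverse event counts over a common fixed window. Fixed windows of 30 and 60 days from first dose appear only for deaths (SAP 11.2).

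**The concern.** The percentage of subjects with at least one event depends on the hazard and on how long subjects are observed. Here the observation period is set by treatment, and treatment can end sooner in the arm where response is less likely and survival shorter. An effective drug would then show more subjects with an event partly because they stay on treatment longer.

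Protocol 5.6.1 gives the contribution of venetoclax to safety as one purpose of the placebo control, so readers will set the two columns against each other. For events that accrue through treatment, that contrast mixes risk with time at risk, and the planned tables do not let a reader separate the two.

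**Working it through.** **1. The plan's own figure.** The adverse event section states no figure. The survival assumptions that drive the cutoff do reproduce. Required deaths by Schoenfeld's formula, HR 6/11, 2:1 allocation, two-sided 0.05, 90% power:

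(1.960 + 1.282)² / [(2/9) × (ln 6/11)²] = 128.7, so 129 for a fixed design.

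With the interim analysis, 131 deaths are needed, and 133 deaths give 90.4% power. The boundaries come out at 0.0097 and 0.0221 against the SAP's 0.010 and 0.022. The design is therefore a sound base for the illustration.

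**2. Inputs.**
- From the documents: survival medians of 6 and 11 months, 70 and 140 subjects, cutoff at the 133rd death, window to last dose + 30 days.
- Assumed: a constant hazard of 5% per month in both arms; median exposure of 6 v 11 months (borrowed from the survival medians, so a high case) or 3 v 5 months; uniform accrual over 6 to 24 months.

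**3. Simplest calculation: exponential treatment duration, no tail, unlimited follow-up.** Crude percentage = λ/(λ + ln2/median), λ = 0.05.
- 6 v 11 months: 0.05/(0.05 + 0.1155) = 30.2% v 0.05/(0.05 + 0.0630) = 44.2%.
- 3 v 5 months: 0.05/(0.05 + 0.2310) = 17.8% v 0.05/(0.05 + 0.1386) = 26.5%.

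**4. Add the 30-day tail** (30/30.44 = 0.986 month). Crude percentage = 1 − exp(−0.05 × 0.986)/(1 + 0.05 × median/ln2).
- 6 v 11 months: 1 − 0.952/1.433 = 34% v 1 − 0.952/1.794 = 47%.
- 3 v 5 months: 1 − 0.952/1.216 = 22% v 1 − 0.952/1.361 = 30%.

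**5. Add the cutoff and death.** This step was simulated. Survival is exponential at the planned medians, and each subject's window closes at the earliest of last dose + 30 days, death, or the date of the 133rd death. The assumed median exposure includes treatment ended by death.

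| Assumed median exposure | Placebo + LDAC | Venetoclax + LDAC | Gap |
|---|---|---|---|
| 6 v 11 months | about 25-27% | about 33-34% | 7-8 points |
| 3 v 5 months | about 18-19% | about 25-26% | 6-7 points |

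The ranges cover accrual of 6 to 24 months. The cutoff narrows the gap because it truncates the longer-treated arm more. If exposure is drawn separately from survival, so that death does not close the window, the levels shift to 28-30% v 35-36% and 20-21% v 26-27%, but the gaps stay at about 7 and 6 points.

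**6. Dependence on the exposure ratio** (tail included, cutoff ignored, so on the high side). For an event seen in 20% of control subjects, with control median exposure of 2 to 6 months, the venetoclax percentage is 22.9-23.4% at a ratio of 1.25, 25.6-26.6% at 1.5, 28.9-30.4% at 11/6, and 34.7-37.0% at 2.5.

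**7. Early events.** If an event can occur only in the first 28 days, the result is 20% v 20%: no inflation.

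**8. Check of the remedy.** With a constant equal hazard, first events per 100 patient-months at risk are 5 in each arm, as they should be. With an equal 20% risk confined to the start of treatment, the same rate gives about 3.6 on placebo v 2.7 on venetoclax (6 v 11 months, with cutoff). That wrongly favors venetoclax, because the extra months add person-time without risk.

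**The case against.** **Crude percentages are conventional, and the tables are descriptive.** They correctly describe risk over the treatment actually given, the SAP follows the protocol, and no test is planned. All of this stands, so there is no error or contradiction in the plan. But leaving out a test does not remove the effect of unequal time at risk from the side-by-side contrast.

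**Longer exposure on venetoclax is not stated.** Correct. It is an inference from open-ended treatment, stopping for treatment failure, the expected response difference and the survival medians. Stopping for toxicity could work against it. The exposure medians used above are assumptions.

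**Not every event accrues.** This stands. Protocol 6.1.7 notes that cytopenias in Cycles 1 and 2 may reflect marrow involvement by AML, and TLS is an early event. The any-event and grade 3 or higher totals may also be near their ceiling: Protocol 3.0 reports grade 3 and above events in 96% of the 25 subjects in the earlier LDAC combination study.

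**Context is already planned.** Exposure by arm, early deaths and regular IDMC safety review (SAP 4.4) all help. They do not allow an adjustment: the duration table covers venetoclax/placebo only, whereas the window follows the later of the two drugs plus 30 days, and time to first event cannot be recovered from an exposure table.

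**Conclusion.** The point holds in a limited form. Adverse events are presented only as crude percentages over a treatment-dependent window. If treatment lasts longer on venetoclax, events with a hazard that persists through treatment will show a higher percentage there at equal hazards. For a 5% monthly hazard the gap is about 6 to 8 points, given the assumed exposure medians and accrual and the documented tail and cutoff.

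A reader might infer more than this, in three ways the documents do not support:
- **A gap of 9 to 14 points.** That follows from unlimited follow-up with no tail (step 3). SAP 6.0 stops safety data at the same cutoff as efficacy, which lowers it.
- **Inflation of all adverse events.** Events confined to Cycle 1 show little or none.
- **A biased formal safety comparison.** No such comparison is planned; the issue is how a descriptive contrast will be read.

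This is an inexpensive improvement to reporting and not a flaw that threatens the trial's conclusions.

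**What to change.** Keep the percentage tables in SAP 11.1 and add, by arm:

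1. First events per 100 patient-months at risk, over the same window (first dose to last dose + 30 days), for serious events and for the Table 9 events that can recur through treatment.
2. For all Table 9 events, including TLS, either a table over a common fixed window (for example the 30 and 60 days from first dose that SAP 11.2 already uses for deaths) or a cumulative incidence with death as a competing event.

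The second item is needed alongside the first: person-time rates assume a roughly constant hazard and can mislead in the opposite direction for early events, as step 8 shows.

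The cost is a few extra tables from event onset and dosing dates already collected. Protocol 1.1 reports that the final analysis has been completed, so any tables added now should be labeled supplementary.

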11.2 Deaths

The number of subject deaths will be summarized (1) for all deaths in this study regardless of the number of days after the last dose of study drug, (2) for deaths occurring within 30 days of the first dose of study drug, (3) for deaths occurring within 60 days of the first dose of study drug, (4) for deaths occurring within 30 days of the last dose of

study drug, and (5) for deaths occurring more than 30 days of the last dose of study drug. There will be no statistical comparison for above analyses.

11.3 Analysis of Laboratory and Vital Signs Data

The value for baseline used in laboratory is defined in Section 6.0. Post baseline visits windows are specified in Table 2. There will be no statistical comparison for laboratory data between two treatment arms.

11.3.1 Analysis of Mean Changes from Baseline in Clinical Laboratory and Vital Signs Data

Changes from baseline will be analyzed for each chemistry, hematology, and vital sign parameters at scheduled post-baseline visits and the final observation (Table 2). Descriptive statistics including mean, standard deviation and median for baseline, and mean, standard deviation, median, minimum and maximum for change from baseline will be presented for baseline, each scheduled post-baseline visit, and final observation by each treatment arm. Laboratory tests to be summarized are included in Table 10 (if data is available).

Table 10. Clinical Laboratory Tests

Hematology	Clinical Chemistry
Hematocrit	Blood urea nitrogen (BUN)
Hemoglobin	Creatinine
Red blood cell (RBC) count	Calculated or Measured creatinine clearance
White blood cell (WBC) count	Total bilirubin
Neutrophils	Serum glutamic-pyruvic transaminase (SGPT/ALT)
Bands (if detected)	Serum glutamic-oxaloacetic transaminase (SGOT/AST)
Blast count	Alkaline phosphatase
Lymphocytes	Sodium
Monocytes	Potassium
Basophils (if detected)	Calcium
Eosinophils (if detected)	Inorganic phosphorus
Platelet count (estimate not acceptable)	Uric acid
Coagulation	Total protein
Prothrombin time (PT)	Glucose
Activated partial thromboplastin time (aPTT)	Albumin
	Lactate dehydrogenase (LDH)
	Chloride
	Bicarbonate

11.3.2 Analyses of Shift from Baseline in Clinical Laboratory Data

For shifts relative to National Cancer Institute Common Toxicity Criteria for Adverse Events (NCI CTCAE version 4.03), baseline and post-baseline laboratory observations will be categorized as grade 0, grade 1, grade 2, grade 3, or grade 4 according to NCI CTCAE grade version 4.03.

The baseline and final grades will be defined respectively as the grade of the last measurement collected on or prior to the first dose of study drug (or randomization for non-treated subjects), and as the last post-baseline measurement collected no more than 30 days after the last dose of study drug.

The maximum NCI toxicity grade value is the value with highest NCI toxicity grade collected after the first dose of study drug and within 30 days following the last dose of

study drug. In cases where multiple values are collected on the same day, the maximum grade value will be selected as the value for that day.

For each variable, shift tables will be generated that cross tabulate the number of subjects with baseline values of grade 0, grade 1, grade 2, grade 3, or grade 4 versus maximum post-baseline/final observations of grade 0, grade 1, grade 2, grade 3, or grade 4. All treated subjects will be included in the cross tabulation regardless whether baseline or post-baseline measurements are collected.

The separate laboratory shifts tables, based on the two criteria below will be generated for each laboratory tests related to CTCAE:

1. Shifts from Grade 0 (Normal) at baseline to grade 1 - 4 Post-baseline (maximum) and worsening from an abnormal baseline value of at least one grade up post-baseline (maximum)
2. Shifts from Grade 0 - 2 at baseline to grade 3 or 4 Post-baseline (maximum) and from grade 3 at baseline value to Grade 4 post-baseline (maximum).

Detailed listings of data for subjects experiencing NCI CTCAE grade 3 to 4 blood chemistry and hematology values will be provided. All measurements collected, regardless of the number of days after the last dose of study drug will be included in these listings.

Number and percentage of subjects with liver Enzyme value meeting the criteria for potential drug-induced liver injury ($ALT > 3 \times ULN$ or $AST > 3 \times ULN$ and $TBILI > 2 \times ULN$ within 72 hours of each other) will be presented.

Number and percentage of subjects meeting the Howard criteria for Laboratory TLS will be presented. Laboratory TLS requires two or more metabolic abnormalities must be present during the same 24-hour period. The evaluation period for TLS is after the first dose of study drug during Cycle 1 until 7 days from the first dose of study drug.

- uric acid > 476 mcmol/l,
- potassium > 6 mmol/l,
- inorganic phosphorus > 1.5 mmol/l
- calcium < 1.75 mmol/l.

